## 6.5 Description and justification of route of administration and dosage

In patients with a renal transplantation, the starting dose is 6 mg orally and then 2 mg once daily. After a week a first trough level assessment is done. The aim in these patients is to obtain a trough level of 12-20 ng/ml in full blood (24). The current practice in the AMC is a target dose of 5-8 ng/ml for patients with a renal transplantation as this results in less adverse events compared to a trough level of 12-20 ng/ml but still results in a clinical effect. As safety and efficacy of this drug has not yet been assessed in patients with FAP, the target range in this study is therefore set at 5-8 ng/ml as recommended by an AMC renal transplantation expert. The starting dose is 2 mg once daily. On day 7 the first trough level is measured and if not within the target range, dosing adjustments are made. In case of dosing adjustments, the next trough level is measured seven days later and this is repeated weekly until the target range is achieved. In case trough levels are within the target range, the next trough level measurement is at month 3, after which dosing adjustments are made if needed, and at month 6. The maximum daily dose is 40 mg.

#### 6.6 Dosages, dosage modifications and method of administration

See chapter 6.5

## 6.7 Preparation and labelling of Investigational Medicinal Product

Sirolimus will be provided free of charge by Pfizer. Labelling of sirolimus will be done by the AMC Hospital Pharmacy according to GCP guidelines (GCP and GMP-annex 13). The registered product Sirolimus will be used, meaning that the accessory label text of the producer will be used. This will be added with another label that indicates: name of the study, name of the principal investigator, name of the sponsor (AMC, [name], [contact]),

Version number: ,date 20 of 40

"uitsluitend ten behoeve van klinisch onderzoek", "Buiten bereik van kinderen bewaren", "Gebruiken volgens voorschrift studieprotocol", patient number, patient name.

## 6.8 Drug accountability

As described in chapter 6.7, sirolimus will be delivered at the AMC Hospital Pharmacy by Pfizer. Sirolimus will be stored and dispensed on a patient named basis by the AMC Hospital Pharmacy and drug accountability of receipt, dispensed, returned and destroyed medication will be kept conform GCP guidelines.

Version number: ,date 21 of 40

#### 7. METHODS

## 7.1 Study parameters/endpoints

#### 7.1.1. Main study parameter/endpoint

- Size of 5 marked polyps in 5 patients with FAP and a large intestinal polyp burden
- Safety outcomes reported by summary analysis of adverse events, clinical laboratory abnormalities and regular physical examination

## 7.1.2. Secondary study parameters/endpoints (if applicable)

- Number of polyps
- Global polyp burden (see definition in chapter 7.2)
- Histology (tubular, tubulovillous or villous histology and degree of dysplasia)
- Patient reported quality of life using HRQoL questionnaires
- Rate of cell proliferation in healthy intestinal mucosa and adenomatous tissue
- Immunohistochemistry of mTOR targets (such as eEF2 kinase, phospho-S6) in healthy intestinal mucosa and adenomatous tissue

#### 7.2 Study procedures

## Baseline and follow-up measurements and monitoring

- -Medical history and physical examination (including vital signs) at baseline and at three monthly visits
- -Lab testing at baseline and at three monthly visits: pregnancy test, urine specimen, hemoglobin, thrombocytes, cholesterol, triglycerides, glucose, potassium, phosphate, calcium, LDH, ALAT, ASAT, GGT, AF, leukocytes, creatinine, albumin.
- -Three monthly HRQoL questionnaires
- -Trough level testing of sirolimus (using the LC-MS/MS method) on day 7 after start study drug and weekly until the therapeutic range has been achieved, after which the next trough level will be measured at three months
- -Monthly telephone check-ups to assess the occurrence of (non-)serious adverse events

Version number: ,date 22 of 40

-LGI endoscopies at baseline and at six months. Endoscopic procedures will be performed after bowel preparation with sedation according to the standard of care by experienced endoscopists.

#### Baseline LGI endoscopy

A video record will be made of the endoscopic examination, which will be conducted in a spiral fashion. Disease stage will be assessed according to the IPSS stage. Polyps >10mm and other relevant polyps can be managed at the discretion of the endoscopist. In all patients, 5 polyps between 3-10 mm will be photographed (with an open biopsy forceps visible), measured (using the open biopsy forceps), and marked using tattoo dye (using SPOT™ 1 cm from the polyp at 9 o'clock, without NaCL and a maximum of 0.5cc SPOTTM), photographed with ink marking, and 5 biopsies of normal mucosa and one biopsy of 5 other adenomatous polyps (other than those marked for the primary outcome measure) will be taken in order to evaluate histology and to measure the rate of cell proliferation and immunohistochemistry. The 5 marked polyps need to have an endoscopic adenomatous appearance, as sirolimus is expected to cause regression of adenomas (and not hyperplastic lesions) (14, 17). There is no evidence concerning the minimum or maximum size of adenomas that could be influenced by sirolimus. We chose not to include adenomas >10mm as we would usually resect them due to an increased risk of developing cancer (33). We chose a minimum size of 3mm as it is our experience that these patients tend to have many small (1-2mm) polyps and by choosing to mark these small polyps, it might be difficult to recognize the marked polyp amongst the adjacent small polyps.

#### Follow-up LGI endoscopy:

A video record will be made of the endoscopic examination, which will be conducted in a spiral fashion. Disease stage will be assessed according to the IPSS stage. The follow-up LGI endoscopy will be conducted in a similar fashion to the baseline examination. All marked polyps will be photographed and measured. Five biopsies of normal mucosa and biopsies of 5 adenomatous polyps (other than those marked for the primary outcome measure) will be taken in order to evaluate histology and to measure the rate of cell proliferation and immunohistochemistry. At the end of the study, histology of adenomatous polyps will be reviewed by an expert GE pathologist.

The above endoscopies are part of routine care. However, extra biopsies that are taken and the tattoos are study related.

Version number: ,date 23 of 40

#### Assessment of degree of polyposis

For the primary outcome measure, the size of polyps will be measured as follows:

## 1. Size of polyps:

The polyp-size is estimated by the endoscopist using the open biopsy forceps (the most reliable method currently available). Two independent reviewers will also assess polyp size of marked polyps at the LGI endoscopy by viewing matching still images per patient on dual monitors. They are blinded for timing of endoscopy (baseline or follow-up). The mean size per polyp is calculated from the assessments of the three reviewers. If the assessment of the reviewers differs by more than 3mm from the assessment of the endoscopist, consensus is needed.

For the secondary outcome measures, the degree of polyposis will be measured as follows:

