As described in chapter 6.2, a significant polyp reducing effect of sirolimus is to be expected. The patients that will be included, are likely to undergo a subtotal colectomy with ileoanal pouch anastomosis or an end ileostomy on a short term base due to the severity of polyposis. These invasive types of surgery are accompanied with a significant risk of comorbidities (29). Even after surgery, patients will develop polyps in the remaining intestinal tissue and therefore surveillance sigmoidoscopies are needed to prevent the development of cancer (5, 30-32). There is currently no alternative treatment available for these patients. Therefore, a medical treatment to postpone or even prevent surgery could be beneficial. If a polyp reducing effect is shown, this therapy could possibly also be beneficial in postponing a preventive colectomy in patients with FAP who have their colon in situ and in postponing a duodenectomy in patients with severe duodenal polyposis.

Version number: ,date 18 of 40

Table 1. Side-effects of sirolimus (SPC)

System/organ	Very frequent	Frequent	Less frequent	Seldom
	(≥1/10)	(≥1/100 to <1/10)	(≥1/1000 to <1/100)	(≥1/10.000 to <
Infections	Pneumonia Fungal infection Viral infection Bacterial infection Herpes simplex infection Urinary tract infection	Sepsis Pyelonephritis CMV infection Herpes zoster infection	Clostridium difficile colitis Mycobacterial infection (incuding tuberculosis) EBV viral infection	
Neoplasms, benign, malignant and non-specified (including cysts and polyps)		Skin cancer	Lymphoma/ post- transplantation lymphoproliferative conditions	
Blood and lymphatic disorders	Thrombocytopenia Anemia Leukopenia	Hemolytic-uremic syndrome Neutropenia	Pancytopenia Thrombotic thrombocytopenic purpura	
Hepatic and biliary disorders			Hepatic failure	
Immune system disorders		Hypersensitivity disorders such as anaphylactic/anaphylactoid reactions, angio-edema		
Feeding and metabolic disorders	Hypokalemia Hypophosphatemia Hyperlipidemia (such as Hypercholesterolemia) Hyperglycemia Hypertriglyceridemia Diabetes mellitus			
Nervous system disorders*	Headache			
Cardiac disorders	Tachycardia	Pericard effusion		
Vascular disorders	Lymphocele Hypertension	Venous thrombosis (such as deep venous thrombosis)	Lymphedema	
Respiratory, chest and mediastinal disorders		Pulmonary embolism Pneumonitis Pleural effusion Epistaxis	Pulmonary hemorrhage	Alveolar protein

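### The primary polyp-size change averages two blinded readings with one that is almost certainly unblinded, and no blinded-only result is planned beside it

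*Combined protocol and SAP*

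**What the plan says.** Section 7.2, under Size of polyps, sets out three readings of each marked polyp. The first is live: "The polyp-size is estimated by the endoscopist using the open biopsy forceps (the most reliable method currently available"). The other two come from independent reviewers of matched still images, of whom the protocol says: "They are blinded for timing of endoscopy (baseline or follow-up"). The readings are then combined: "The mean size per polyp is calculated from the assessments of the three reviewers". The parallel rule under Number of polyps averages all three assessments, which confirms that the endoscopist is the third. Large disagreements are handled by one sentence: "If the assessment of the reviewers differs by more than 3mm from the assessment of the endoscopist, consensus is needed".

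Under Baseline LGI endoscopy the five polyps are "measured (using the open biopsy forceps), and marked using tattoo dye". Under Follow-up LGI endoscopy, "All marked polyps will be photographed and measured".

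Section 5.1 gives every patient sirolimus without placebo. Section 6.4 states that "a significant polyp reducing effect of sirolimus is to be expected", and the choice of adenomatous-looking polyps is justified "as sirolimus is expected to cause regression of adenomas". Sections 9, 9.1 and 9.2 plan descriptive summaries of change and do not mention results by assessor.

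**The concern.** The sponsor arranged blinded image reading for the primary endpoint, but the only size result it commits to report blends those readings with one made at the bedside. Whoever performs the six-month endoscopy must find polyps that already carry a tattoo, so that person almost certainly knows which visit it is. Everyone is on active drug and regression is expected. If the expectation lowers the live reading at follow-up, part of that shift appears as a drug effect.

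Without a control arm, the blinded readings are the main protection against this. Once they are averaged with the live reading, a reader of the results cannot tell whether a small regression was also seen blind.

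**Working it through.** The plan has no figure to reproduce: section 4.4 gives no sample size calculation, and no measurement SD or bias is stated. The weights follow from section 7.2. The bias and SD values below are assumptions.

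**1. Weight and bias.** Let E be the endoscopist's reading and R1 and R2 the image readings. The planned size is M = (E + R1 + R2)/3. If the endoscopist's bias is a0 at baseline and a1 at follow-up, its contribution to the change in M is (a1 − a0)/3, provided consensus is not triggered. If a1 = a0 the contribution is zero. Write b for the size of the difference a1 − a0. Marked polyps are 3 to 10 mm, so the mid-window size is (3 + 10)/2 = 6.5 mm.

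| b (assumed) | shift in planned change, b/3 | as % of 6.5 mm | direct shift in blinded-only change |
|---|---|---|---|
| 0.5 mm | 0.17 mm | 2.6% | 0 |
| 1 mm | 0.33 mm | 5.1% | 0 |
| 2 mm | 0.67 mm | 10.3% | 0 |

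The last column is for B = (R1 + R2)/2, in which E has no weight. It assumes that the image reviewers stay blind and that the images carry none of the bias.

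**2. Limit set by the 3 mm rule.** Suppose all three agree at baseline and both image reviewers see no change. The endoscopist can then read exactly 3 mm lower at follow-up without triggering consensus, and M falls by 3/3 = 1.0 mm. A 5 mm polyp would be recorded as (2 + 5 + 5)/3 = 4.0 mm. This is a bound, not an expected bias.

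**3. Precision of the blinded-only change.** Take reviewer variance as the unit, rho as the correlation between the two reviewers' errors, s as endoscopist SD divided by reviewer SD, and endoscopist errors as independent of the reviewers'. Then var(M) = (2 + 2·rho + s²)/9 and var(B) = (1 + rho)/2. For the mean change over 5 × 5 = 25 polyps, with readings independent across polyps and visits, multiply each by 2/25. The bias at which the two results have equal total error is 3·√(difference of these two variances). With reviewer SD 1.0 mm:

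| rho, s | var(M) | var(B) | SD ratio B/M | SD of mean change, M | SD of mean change, B | break-even b |
|---|---|---|---|---|---|---|
| 0, 1 | 0.333 | 0.500 | 1.22 | 0.16 mm | 0.20 mm | 0.35 mm |
| 0.5, 1 | 0.444 | 0.750 | 1.30 | 0.19 mm | 0.24 mm | 0.47 mm |
| 0.5, 0.5 | 0.361 | 0.750 | 1.44 | 0.17 mm | 0.24 mm | 0.53 mm |

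Below the break-even bias the planned mean is the better estimate; above it the blinded-only mean is. At reviewer SD 2.0 mm the break-even range doubles, to 0.69 to 1.06 mm.

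**4. Secondary endpoints.** Number of polyps and global polyp burden also average three assessors. An assumed endoscopist bias of 10 polyps at one visit moves the change in count by 10/3 = 3.3, and a 1-point bias in the burden score moves it by 1/3 = 0.33.

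**The case against.** The case for leaving the plan alone is substantial. The protocol gives a reason for including the live reading: it regards forceps sizing as the best method available. Two thirds of the weight is blinded, and the 3 mm rule flags an endoscopist far from the image reviewers. The planned mean has the lower total error when the between-visit bias is small, and nothing in the documents says that it is large. The study is explorative, with five patients and no decision rule. All of this stands. It is why the three-assessor mean should remain primary and why the point is minor. It does not explain why the blinded readings should go unreported on their own.

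A second objection is that the blinded-only result may not be fully blind. Baseline photographs are taken both before and after the ink, section 7.2 does not say which are shown, and a picture without ink would reveal the visit. The images are also framed, with the forceps placed, by the endoscopist, so some bias could carry over. The first problem can be avoided by choice of image; the second remains a limitation.

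A reader might go further and infer that the planned mean would show regression in nearly every trial of an inactive drug. With a uniform 1 mm bias, SD 1.0 mm, no consensus and no variation between patients, the illustrative figure is 96% to 98%. It falls to about 85% at 0.5 mm of bias. With 1 mm of bias and a between-patient SD of 0.5 or 1 mm, it is about 89% or 76%. The documents support none of these inputs.

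A reader might also infer that the undefined consensus step inflates the bias. That depends on who prevails and on independent errors. At SD 1.0 mm and 1 mm of bias, consensus is triggered in 2% to 14% of follow-up readings under independence, but in only 0.4% to 4% if endoscopist and reviewer errors correlate at 0.5.

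**Conclusion.** The concern holds as a minor reporting gap. The one-third weight is arithmetic. The endoscopist's knowledge of the visit is an inference from the tattooing and re-measurement, not something the protocol states. The resulting shift is b/3 for a bias b that differs between visits, and the documents do not give b.

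The documents do not support calling the planned endpoint invalid, removing the endoscopist's reading, or accepting a drug effect only when the blinded change points the same way. The last would add a decision rule to a descriptive pilot. Nor do they support letting the image reviewers' value replace the mean after a disagreement. That would discard the reading the protocol trusts most exactly where it differs.

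The protocol does not say who takes part in consensus, whether one, both or the average of the reviewers is compared with the endoscopist, or what value results. This is missing detail. It matters here only because a blinded-only summary must use readings recorded before consensus.

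**What to change.** In sections 7.2 and 9.1, keep the three-assessor mean as the primary result and add:

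> *The change based on the two blinded reviewers alone and the change based on the endoscopist alone, both from readings recorded before any consensus, are reported beside it.*

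In section 9.2, report number of polyps and global polyp burden by assessor in the same way. For global burden, use each assessor's single relative score per patient. In section 7.2, state that the image reviewers are shown photographs with ink marking from both visits, so that absence of ink does not give away the baseline.

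The cost is a few sentences and two extra descriptive results per endpoint, with no new readers, images or visits. The blinded-only change will be noisier, with a random-error SD 1.22 to 1.44 times that of the planned mean under the assumptions above, and should be presented as such.

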#### 2. Number of polyps:

During endoscopy, the number of polyps is estimated by the endoscopist. At a later phase, two independent reviewers will also assess the number of polyps seen (categorized per 10 polyps) by viewing both videos (before and after treatment) per patient, blinded for the order. The mean number of polyps is calculated as a mean of all 3 assessments. If the assessment between reviewers differs by more than 10 polyps from the assessment of the endoscopist, consensus is needed.

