#### 5.2 Use of co-intervention

Female participants who are sexually active must use adequate contraception as confirmed by three monthly pregnancy tests and male patients need to use adequate contraception as well. Adequate contraception needs to be continued until 12 weeks after therapy. Furthermore, any new concurrent medication that is started during the study needs to be reported. If known to have an interaction with sirolimus, an additional trough level measurement needs to be done. Patients will visit the AMC at baseline, month 3 and month 6 for the interventions as mentioned in chapter 1 'Study design' (physical examinations, laboratory tests, pregnancy test, urine specimen , questionnaires) and weekly for sirolimus trough level testing until the target range has been achieved. Moreover, monthly telephone check-ups will be performed.

Endoscopies that take place at baseline and at 6 months follow-up are not considered cointerventions, as these are performed in a frequency that is consistent with our practice guidelines. Tattoos that are placed during these procedures are considered additional interventions and biopsies that are done can partly be considered as additional interventions, as some of these would have been done in routine care: 5 biopsies of normal mucosa are additional, 5 biopsies of adenomatous tissue are part of routine care.

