## 3. Global polyp burden:

During endoscopy, the global polyp burden is estimated by the endoscopist. At a later phase, two independent reviewers will also globally assess polyp burden by viewing both videos per patient, blinded for order. The second video in the pair could take the value of –2 (much better), –1 (better), 0 (same), 1 (worse) or 2 (much worse) relative to the first video. Mean scores are calculated for each subject and averaged for the three reviewers. If the assessment of the reviewers differs by more than 1 point from the assessment of the endoscopist, consensus is needed.

Version number: ,date 24 of 40

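### Section 7.2 does not say how order-blinding of the endoscopy videos survives the tattooing done during the filmed baseline examination

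*Combined protocol and SAP*

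**What the plan says.** All of this is in section 7.2 of the combined protocol and SAP unless stated.

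- **Number of polyps.** Two readers count "by viewing both videos (before and after treatment) per patient, blinded for the order". A third value is obtained live: "During endoscopy, the number of polyps is estimated by the endoscopist". The three values are averaged.
- **Global polyp burden.** Here "two independent reviewers will also globally assess polyp burden by viewing both videos per patient, blinded for order", on a scale from -2 to +2. The endoscopist again gives a live assessment, and the three scores are averaged.
- **Consensus.** It is required when the readers are more than 10 polyps, or more than 1 point, away from the endoscopist.
- **Baseline LGI endoscopy.** "A video record will be made of the endoscopic examination, which will be conducted in a spiral fashion". In the same examination five polyps per patient are measured, "marked using tattoo dye" and then "photographed with ink marking".
- **Follow-up LGI endoscopy.** This examination is filmed too. "All marked polyps will be photographed and measured". No new tattooing is described.
- **Section 5.2.** After naming the baseline and 6-month endoscopies together, it is looser: "Tattoos that are placed during these procedures are considered additional interventions".

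The documents give no start or stop point for the recording relative to the tattooing, no editing or masking of the videos, and no check on whether the blinding held.

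**The concern.** The plan promises readers who do not know which video came first. It also has the investigators place a visible, lasting mark during the first of the two filmed examinations. A reader who sees bare mucosa being injected, or who sees ink in one video and not in the other, knows the order.

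This matters because the study has no control group (section 5.1: no placebo) and section 6.4 says that a polyp-reducing effect is expected. Both outcomes are visual judgements: a count in categories of ten and a better-or-worse score. Blinding to order is the main guard against expectation in those judgements. The endoscopist's reading does not share it, because a live estimate is made with the time point known. If the two readers can also tell the order, none of the three averaged readings is blinded.

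The point concerns the videos only. Polyp size, the primary efficacy outcome, is read from still images, and changing how the stills are paired would leave the videos as they are.

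**Working it through.** The plan states no figure to reproduce: section 4.4 has no sample size calculation and section 9 is descriptive. The check is a comparison of the text followed by simple weighting.

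**Step 1. What each video can show, by recording option**

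| Option for the baseline recording | Baseline video | Month-6 video | Order revealed? |
|---|---|---|---|
| (a) Made before tattooing | No study ink | Ink from the outset | Yes |
| (b) Whole examination, including tattooing | Unmarked mucosa, then injection | Ink from the outset, no injection described | Yes |
| (c) Starts, or is cut to start, after all five marks | Fresh ink | Healed ink | Not necessarily |

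Option (b) is the plain reading of the filming sentence, which takes in the examination without qualification. Option (c) is not excluded, but no section specifies it.

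**Step 2. Does section 5.2 change this?** Suppose its looser wording means that ink is also placed at month 6. The month-6 video would still show the earlier marks from the start, and under (a) or (b) the baseline video would not. The order remains readable.

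**Step 3. Weight of the two readers in the mean.** Three equally weighted readings give each a weight of 1/3. Let b be the amount by which knowing the order moves a reading.

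- Only the endoscopist biased: shift = b/3.
- All three biased by b: shift = 3 × b/3 = b.
- Added by the two readers losing their blinding: b − b/3 = 2b/3.

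**Step 4. Illustration only.** The documents give no value for b, so the values below are assumptions.

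- Global burden, b = 0.5 point: 0.5 × 2/3 = 0.33 point.
- Global burden, b = 1 point: 1 × 2/3 = 0.67 point.
- Polyp count, b = one category of 10: 10 × 2/3 = 6.7 polyps. This is 6.7/25 = 27% at 25 polyps, 6.7/50 = 13% at 50 and 6.7/100 = 7% at 100. Section 4.2 requires more than 25 polyps at entry, so 27% lies at the edge of the eligible range.

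**Step 5. Would consensus catch it?** If the readings would otherwise agree and the endoscopist were unbiased, a gap of exactly 1 point or 10 polyps would not exceed either trigger. If the endoscopist leaned the same way, the gap would be zero. Where consensus is triggered, the comparison is with the unblinded reading, and the plan does not say how the agreed value enters the mean. The figures in step 4 therefore apply before any consensus step.

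**The case against.** The strongest reply is that the plan is silent here rather than wrong. Nothing in 7.2 prevents a recording or an edited clip that starts after all five marks are in place, so that both videos show ink. A reader might infer that the two outcomes will be read unblinded, or that the order is visible whatever is done. The documents do not support that: option (c) is compatible with the text, and it is the remedy proposed below.

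Other points on that side:

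- **There are other safeguards.** Two independent readers, averaging and a consensus rule are planned, so order-blinding is not the sole protection. That is fair, but none of them removes an expectation that all readers share, and consensus is anchored to the endoscopist.
- **The stakes are limited.** These are secondary outcomes in five patients, analysed descriptively, with no test or decision rule attached. This stands and limits the weight of the point.
- **The endoscopist's third is unblinded whatever the ink shows.** This also stands. It is a reason to report the two readers' mean on its own.
- **Ink is not the only cue.** At baseline the endoscopist may manage larger and other relevant polyps at discretion, and a fresh removal site could also give away the order. The fix has to cover this.

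What does not stand is that this is only a missing detail. Filming the examination as the text describes it would defeat a safeguard that the same section states.

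**Conclusion.** The point holds in this form: order-blinding of number of polyps and global polyp burden is not secured by the plan as written, and on the plain reading it probably fails. It is not established that it will fail, since the timing and editing of the clips are unspecified.

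No size can be taken from the documents. A bias b shared by the two readers shifts the three-reader mean by 2b/3 before consensus, assuming equal weights and the same b for both. The 0.33 to 0.67 point and 6.7 polyp figures only illustrate assumed values of b. No error rate or power figure is affected, and the still-image reading of polyp size is outside this point. The change is worth making because it is cheap and because, if the readers can tell the order, neither outcome has a blinded reading left.

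**What to change.** In section 7.2, for both examinations:

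1. Define the reader clip as a single pass recorded, or cut to begin, only after all five marks are in place.
2. End the clip before the study biopsies and, where the endoscopist's discretion allows, before any polyp removal. Otherwise, state that segments showing fresh removal sites are handled in the same way in both clips. The discretion itself is left as it is.
3. Remove dates and sound.
4. After scoring, have each reader record a guess of the order, and report the share correct beside both outcomes. Two readers and five patients give 2 × 5 = 10 guesses, of which 5 would be right by chance on average. A real treatment effect can also help a reader guess correctly, so the share should be interpreted with that in mind.
5. Report the two readers' mean separately, beside the three-reader mean.

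**Cost.** A small change in the endoscopy sequence, light editing of 5 × 2 = 10 videos and one extra question for readers already in the plan. No extra staff or procedure is needed. The downside is that blinding may remain partial, because fresh and healed ink can look different; the guess question would help to show how far.
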